10.1.2 Stop dates (e.g., AE resolution date or stop date of medication)

- For missing stop day only - Day will be imputed as the last day of the month (i.e., 28, 29, 30, or 31)
- For missing stop day and month - Day and month will be imputed as the last day of the year (i.e., 31 December)

Any partial dates will be displayed in data listings without imputation of missing days and/or months (e.g., MAR2011, 2009). No other imputation of missing data will be performed.

No imputation methods will be used for analysis of missing efficacy data in this study.

10.2 Definition of Baseline

For all endpoints, baseline is defined as the last non-missing measure or the average of the non-missing measures before the first dose of study drug. Change from baseline to follow-up visit will be calculated as the baseline measurement subtracted from the follow-up measurement for all assessments with the exception of the CPET endpoints. The first measurements for CPET endpoints occur at Study Day 2. The change from Day 2 to Day 29 will be calculated as the Day-2 measurement subtracted from the Day-29 measurement for all CPET endpoints.

The percent change from baseline values to post-baseline values will be calculated using the following formula where applicable:

$$([\text{post-baseline value} - \text{baseline value}] / \text{baseline value}) \times 100\%$$

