	
Safety laboratory assessments include: hematology, serum chemistry, urinalysis, coagulation panel, Hepatitis A, B, C and HIV serologies and pregnancy tests.
 
Clinical Assessments
 
Spirometry and Diffusing Capacity of the Lung for Carbon Monoxide (DLco) Measurements
 
All equipment, procedures, and personnel qualifications for the assessment of lung function are based on the recommendations of the American Thoracic Society (ATS 2005) and will be performed at each site using local equipment. Spirometry measurements will include FVC, FEV₁ and flow-volume loops. Pre and post-bronchodilator assessments will not be performed. DL_{CO} will be measured at each site by determining the diffusing/transfer capacity of the lung for carbon monoxide
 
Oxygen Saturation
 
During screening and with all scheduled vital sign assessments resting, room air oxygen saturation (SpO₂) will be measured by pulse oximetry (provided by the Sponsor) whilst the subject is seated and resting for at least 5 minutes. Before recording the SpO₂ value in the eCRF the study staff should ensure the measurement is stable, which may require continuous or repeated measurements and ensuring the subject is resting. SpO₂ will be also be collected as part of the 6MWT and during cardio-pulmonary exercise testing.
 
6-Minute Walk Test (6MWT) and Borg Scale of Perceived Exertion
 
Functional exercise capacity will be evaluated at baseline, Days 15, 28 and 58 using the 6-minute walk test. The 6MWT will be performed without the subject using supplementary oxygen. Oxygen may be used at any time during the 6MWT, if in the opinion of the Investigator or testing technician it is required for safety reasons. The 6MWT should then be stopped.
 
Guidelines developed by the ERS/ATS will be used for conducting the test and interpreting the results (ATS 2002 and Holland 2014).
 
As part of the 6MWT SpO₂, heart rate and the Borg dyspnea scale will be measured prior to starting the test, during the test, at completion of the test, 1 minute and 2 minutes after test completion.
 
Cardiopulmonary Exercise Testing (CPET)
 
Symptom-limited cardiopulmonary exercise testing using a bicycle ergometer will be performed at baseline and Day 29. At baseline and during the exercise period the collected data will include but is not limited to: SpO₂ and arterial blood gases, VO₂ max, ventilation and lactate thresholds. Guidelines developed by ATS and American College of Chest Physicians will be used for conducting the test and interpreting the results (ATS 2003).
 
St George's Respiratory Questionnaire (SGRQ)
 
The SGRQ is a symptom-specific 2-part, subject self-administered questionnaire that assesses shortness of breath while doing a variety of activities of daily living. This questionnaire comprises three domains: symptoms, activity and impact. Paper questionnaires will be provided to

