3.2.3. Exploratory Endpoints

- Change and percentage change from baseline in distance walked during the 6MWT at Days 15 and 28.
- Time to first SpO₂ <88% that is sustained for at least 10 seconds during the 6MWT at Days 15 and 28.
- Area under the SpO₂ curve (AUC) during the 6MWT measured at baseline, Day 15 and Day 28.
- Change from baseline in PRO scores using SGRQ, UCSD, A Tool to Assess Quality of Life (ATAQ) in IPF (only subjects enrolled in Part B), and the Borg Scale of Perceived Exertion questionnaires and cough VAS at Days 15 and 28.
- Change and percentage change from baseline in cardiopulmonary exercise testing parameters at Day 29.
- Change and percentage change from baseline in lung function, including FVC and DL_{CO} at Day 28.
- PK/PD relationship in subjects receiving GBT440 from Baseline to Days 15 and 28

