5.5.4. Cardiopulmonary Exercise Testing (CPET)

Symptom-limited cardiopulmonary exercise testing using a bicycle ergometer will be performed on Day 2 and Day 29. At baseline and during the exercise period the collected data will include but is not limited to: SpO₂ and arterial blood gases, VO₂ max, ventilation and lactate thresholds. Guidelines developed by ATS and American College of Chest Physicians will be used for conducting the test and interpreting the results ([ATS 2003](#)).

Instructions for the conduct of the CPET will be provided in a separate manual. An arterial line placement will be part of the CPET procedure. If the subject refuses arterial line placement they may still undergo the CPET assessments without the arterial line.

Agreement to undergo the CPET is not required for entry into the study; but participation is strongly encouraged.

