17.7 Cardiopulmonary Exercise Testing (CPET)

Cardiopulmonary exercise testing (CPET) parameters are computed using data collected on the CRF from all treated subjects at Day 2 and Day 29. The following CPET parameters by stage include:

Stage	CPET Parameters
Rest	HR, Extime, VCO ₂ , VO ₂ , RER, SpO ₂ , Art_O ₂ , Art_O ₂ Sat, Art_CO ₂ , Lactate
VentThrsh	HR, Extime, VCO ₂ , RER, SpO ₂ , Art_O ₂ , Art_O ₂ Sat, Art_CO ₂ , Lactate, VENT/VO ₂
LactThrsh	HR, Extime, VCO ₂ , VO ₂ , RER, SpO ₂ , Art_O ₂ , Art_O ₂ Sat, Art_CO ₂ , Lactate, Watts
Max	HR, Extime, VCO ₂ , VO ₂ , RER, SpO ₂ , Art_O ₂ , Art_O ₂ Sat, Art_CO ₂ , Lactate, Watts

- HR = Heart Rate (bpm)
- Extime = Exercise time (elapsed time from start to end of stage)
- VCO₂ = Carbon Dioxide Excretion (mls/min)
- VO₂ = Oxygen Consumption (ml/min)
- RER = Respiratory Exchange Ratio (VCO₂/VO₂)
- SpO₂ = Oxygen Saturation (%)
- Art_O₂ = Arterial Oxygen (mmHg)
- Art_O₂Sat = Arterial Oxygen Saturation (%)
- Art_CO₂ = Arterial Carbon Dioxide (mmHg)
- Lactate = Lactate Concentration (mmol/L)
- Watts = Exercise Output (Watts)
- VentThrsh = Ventilatory Threshold
- LactThrsh = Lactic Acid Threshold

Summary statistics for the CPET parameters at the following endpoints will be displayed by study drug and for all GBT440 by visit using the Efficacy-Evaluable population. Summary statistics for the change from Day 2 to Day 29 will be included in the summary.

Parameter	Endpoint
Exercise Time (Minutes)	Max – Rest
Watts	Max
VO ₂ (ml/min/kg)	Max
SpO ₂ (%)	Max – Rest
Arterial Oxygen (mmHg)	Max – Rest
Arterial Oxygen Saturation (%)	Max – Rest
Lactate (mmol/L)	Max – Rest
VO ₂ (ml/min/kg)	VentThrsh / Max
Watts	VentThrsh / Max
Heart Rate (bpm)	Rest
Heart Rate (bpm)	Max – Rest
RER	Max
Arterial Carbon Dioxide (mmHg)	Max – Rest
Heart Rate (bpm)	VentThrsh – Rest
Exercise Time (Minutes)	VentThrsh – Rest
VENT/VO ₂ (ml/min/kg)	VentThrsh
SpO ₂ (%)	VentThrsh – Rest
Arterial Oxygen (mmHg)	VentThrsh – Rest
Arterial Carbon Dioxide (mmHg)	VentThrsh – Rest
Arterial Oxygen Saturation (%)	VentThrsh – Rest

VO₂ (ml/min) will be divided by the subject’s last non-missing body weight measurement before each analysis timepoint (ie Day 2 or Day 29) to obtain VO₂ (ml/min/kg).

ANCOVA models will be used to analyze the effect of treatment on the change from Day 2 with the Day-2 value as a covariate. Least squares (LS) means and SEs will be displayed for the change from Day 2 in each treatment group and for all GBT440.

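### No exercise test precedes the first dose, so the promised CPET change from baseline cannot be obtained, and the Day 2 value used instead is post-dose and may attenuate the planned contrasts

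*SAP*

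**What the plan says.** **Schedule.** Protocol 5.5.4 states: "Symptom-limited cardiopulmonary exercise testing using a bicycle ergometer will be performed on Day 2 and Day 29". Protocol Appendix A and SAP 5.1 mark the same two days and no others. The first dose is given on Day 1, and the note to Appendix A puts assessments before that day's dose unless otherwise indicated. The Protocol Synopsis describes the timing differently: "Symptom-limited cardiopulmonary exercise testing using a bicycle ergometer will be performed at baseline and Day 29".

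**Endpoint.** Protocol 3.2.3 lists "Change and percentage change from baseline in cardiopulmonary exercise testing parameters at Day 29", and SAP 3.3 repeats it. The matching objective in Protocol 2.3 also compares Day 29 with baseline.

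**Baseline.** In SAP 10.2, "baseline is defined as the last non-missing measure or the average of the non-missing measures before the first dose of study drug". The same section then treats CPET as an exception ("The first measurements for CPET endpoints occur at Study Day 2") and defines its change as Day 29 minus Day 2.

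**Analysis.** SAP 17.7 fits one ANCOVA per endpoint, to "analyze the effect of treatment on the change from Day 2 with the Day-2 value as a covariate". All four active-minus-placebo contrasts come from it. Descriptive statistics are shown by arm and visit, and "Summary statistics for the change from Day 2 to Day 29 will be included in the summary". No percentage change is planned for CPET.

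**Record of changes.** SAP 19 lists three departures from the protocol. Neither the Day 2 reference nor the missing percentage change is among them.

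**Status.** CPET is exploratory, and Protocol 5.5.4 adds: "Agreement to undergo the CPET is not required for entry into the study".

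**The concern.** The endpoint and the objective describe a comparison with an untreated state that the schedule never measures. Someone who reads the endpoint list and then the CPET tables would take the change as starting from a pre-treatment value.

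The second issue is the covariate. Baseline adjustment is harmless because treatment cannot have affected a pre-dose value. The Day 2 value is measured after randomisation and after one dose. Any effect already present then is removed from the contrast, in part by the ANCOVA and in full by the raw change. A small difference in change from Day 2 could then be read as no effect on exercise capacity, although part of the effect had been subtracted. No Day 29 between-arm estimate with a confidence interval and without the Day 2 value is planned as a check on that reading.

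**Working it through.** The plan gives no sample-size, power or effect figure for CPET, so there is nothing to reproduce. The check is one of timing, followed by an illustration of size.

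**1. Timing.** First dose: Day 1. First CPET: Day 2, before the second dose. Protocol 5.6 times the Day 2 pre-dose visit sample at 24 ± 2 hours after the Day 1 dose. No CPET value can meet the pre-dose definition in SAP 10.2.

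**2. Form of the bias.** Let D be the Day 29 effect, fD the effect already present on Day 2, and b the within-arm slope of Day 29 on Day 2.

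- Raw change from Day 2 estimates D(1 − f).
- The planned ANCOVA estimates D(1 − bf).
- An unadjusted Day 29 comparison estimates D.

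A large-sample simulation agreed with these expressions (for example f = 0.219, b = 0.8: 0.826 simulated, 0.825 by formula).

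**3. Range for f.** The documents give no human half-life, but they imply two upper bounds. Protocol 3.1 treats the 30-day follow-up as at least 5 half-lives: 30/5 = 6 days. Protocol 6.3 treats a visit 2 weeks after the last dose the same way: 14/5 = 2.8 days. Assume one-compartment, once-daily dosing and an effect proportional to trough exposure. Then f = 1 − 2^(−1/t), with t the half-life in days:

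- t = 6: f = 0.109
- t = 2.8: f = 0.219

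Because these are upper bounds on t, they are lower bounds on f under that assumption. The assumption may fail in the other direction. Protocol 1.5.3 expects response from about 20% haemoglobin occupancy and places 11% modification below the level that showed benefit in animals. With t = 2.8, Day 2 modification is 0.219 × 24, 38 and 50 = 5.3%, 8.3% and 11.0% at 600, 900 and 1500 mg. A threshold of that kind would put f near zero.

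**4. Size at the trial's numbers.** Pooling Parts A and B gives 9 on placebo (6 + 3), 9 on 600 mg (6 + 3), 6 on 900 mg and 9 on 1500 mg. Simulation with 40,000 runs per case, 9 v 9, a 1-SD Day 29 effect and a Day 2 to Day 29 correlation of 0.7 (effect size and correlation assumed), in SD units:

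| Quantity | f = 0 | f = 0.11 | f = 0.22 |
|---|---|---|---|
| Planned ANCOVA, mean | 1.00 | 0.92 | 0.85 |
| Planned ANCOVA, RMSE | 0.35 | 0.36 | 0.38 |
| Planned ANCOVA, power | 0.76 | 0.70 | 0.62 |
| Raw change, mean | 1.00 | 0.89 | 0.78 |
| Unadjusted Day 29, mean | 1.00 | 1.00 | 1.00 |
| Unadjusted Day 29, RMSE | 0.47 | 0.47 | 0.47 |

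The ANCOVA's SE is about 0.35. The unadjusted comparison has SE √(2/9) = 0.47 and power 0.51. With no drug effect on either day, both reject at 0.050.

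**5. Break-even.** The unadjusted comparison has the lower RMSE only when 0.7f exceeds about √(0.47² − 0.35²) = 0.31, that is, f above about 0.45. Direct simulation puts the crossing at about 0.44. Under the exposure model in step 3 that needs a half-life below about 1.2 days.

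**The case against.** The strongest reply is that the SAP already deals with this. Section 10.2 says that the first CPET is on Day 2 and defines the change accordingly, section 17.7 repeats it, and SAP section 1 gives the SAP's methods precedence over the protocol's. That stands: the substitution is disclosed, and a reader who inferred a concealed calculation would be wrong. It does not repair the endpoint and objective, which still claim a comparison with baseline, or the silence of SAP 19.

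A second reply is that an unadjusted Day 29 difference can be derived from planned output, because SAP 10.3 and 17.7 give n, mean and SD by arm and visit. That is also true. The missing piece is a prespecified contrast with an interval and a statement of how to read it, not the data.

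Third, nothing in the documents shows an effect on Day 2. Under the exposure model, reaching 20% modification by Day 2 needs a half-life below about 0.4, 0.9 and 1.4 days at 600, 900 and 1500 mg. The 20% figure concerns exercise-induced desaturation and does not settle every CPET parameter, but it is a fair reason not to claim that an effect is being masked.

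Fourth, the numbers favour the planned model. In a four-arm model (9/9/6/9, same assumptions) the ANCOVA does slightly better still at f = 0: SE 0.34 and power 0.81, against SE 0.47 and power of 0.53 to 0.54 unadjusted. This stands, and the ANCOVA should not be replaced.

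Finally, leaving out percentage change is defensible. Thirteen of the 20 endpoints are stage-minus-rest differences, some with denominators that may be near zero, and SAP 10.2 applies percentage change only where applicable. The decision still needs to be recorded.

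**Conclusion.** The point holds, as a minor one. It is certain that no CPET precedes the first dose, that the stated change and percentage change from baseline cannot be obtained under SAP 10.2, and that the documents disagree on this. It is conditional that the contrasts are attenuated: this requires a same-direction effect after one dose and a positive within-arm slope. The loss is then f times that slope, about 8% at f = 0.11 and 15% at f = 0.22 with a slope of 0.7. Over the values of f examined, the bias is smaller than the sampling error. The values of f rest on an assumed exposure model, and the slope and effect size are also assumptions; f may be near zero.

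A reader might infer that the CPET contrasts are invalid or prone to false positives. The documents do not support that: with no drug effect on either day the planned ANCOVA keeps its 0.05 level. Nor do they support the claim that a real effect is being hidden, because f is unknown. The consequences are limited. CPET is exploratory and optional, SAP 3.4 specifies no formal hypotheses, and the primary safety and 6-minute walk analyses are unaffected.

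**What to change.** 1. **Restate and reconcile.** Describe the CPET endpoint and objective as change to Day 29 from a post-dose Day 2 reference. Bring the Protocol Synopsis, Protocol 2.3 and 3.2.3 and SAP 3.3 into line with Protocol 5.5.4 and SAP 10.2 and 17.7. State whether percentage change is dropped or kept, and if kept, for which endpoints. List both points in SAP 19.
2. **Keep the planned ANCOVA as the main CPET analysis and add a check.** For the same four contrasts, report unadjusted between-arm differences on Day 29 and on Day 2, with 95% confidence intervals and no p-values. State that a small change from Day 2 is not evidence of no effect.
3. **Limit the check to endpoints that can be computed.** Two of the 20 endpoints are ratios of ventilatory threshold to maximum, for VO2 and Watts, but SAP 17.7 lists neither parameter at that threshold. The SAP should say how these two will be obtained or omit them.

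The cost is SAP text and table columns, with no new data, visits or procedures, and no change of schedule is proposed. The added intervals are about 35% wider than the ANCOVA's (SE about 0.47 against 0.35 SD at 9 v 9, and 0.53 against 0.39 at 6 v 9, with the assumed correlation of 0.7). They will be wider still if subjects decline CPET. With 18 endpoints, 4 contrasts and 2 days there are 18 × 4 × 2 = 144 of them, and SAP 10.4 plans no multiplicity adjustment. They should therefore carry no p-values and serve only as an aid to interpretation.

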10.3 Data Analysis Conventions

Analyses for SMC meetings, interim analyses, and final data analysis will be performed by Statistics & Data Corporation (SDC). The final data analyses will be performed after Part B of the study is completed and the database has been locked. Data from Parts A and B of the study will be pooled across the common treatment arms (GBT440 600 mg and placebo arms). Statistical programming and analyses will be performed using SAS® Version 9.4 or higher. All study data will be listed by subject, study drug,

and visit (as applicable) based on randomized and treated subjects unless otherwise specified. Summary statistics will be presented by treatment group including all GBT440, and will include a total column where appropriate.

Study visits will be referred to in all tables and listings as the visit name corresponding to the planned study visit.

Summaries for continuous and ordinal variables will include the number of observations (n), arithmetic mean, standard deviation (SD), median, minimum, and maximum). Minima and maxima will be reported with the same precision as the raw values; means and medians will be presented to one additional decimal place than reported in the raw values. Standard deviations will be presented to two additional decimal places than reported in the raw values. Summaries for discrete variables will include frequency counts and percentages. All percentages will be rounded to one decimal place (i.e., XX.X%).

All statistical tests will be two-sided with a significance level of 0.05 ($\alpha = 0.05$) unless otherwise specified. Confidence intervals (CI) for differences between treatment groups will be two-sided at 95% confidence. All p values will be rounded to four decimal places; p-values less than 0.0001 will be presented as “<0.0001”; p-values greater than 0.9999 will be presented as “>0.9999”.

All summary tables will be supported with subject listings.

10.4 Adjustments for Multiplicity

As this is a phase 2 study for which there is no pre-determined power to show a difference to a control, there will be no multiplicity adjustments in this study.

11. Disposition of Subjects

Subject disposition will be presented in terms of the numbers and percentages of subjects who were randomized and completed study treatment, completed the study, and discontinued from the study. Subjects who are not discontinued from the study will be considered study completers. The number of subjects in the Safety and Efficacy-Evaluable populations will be displayed by study drug, and percentages will be calculated using subjects in the Safety population as the denominator.

The number and percentage of subjects prematurely discontinued from the study and the reasons for study discontinuation will be summarized by treatment group for all subjects in the Safety population. The reasons for study discontinuation that will be summarized include: subject withdrawal of consent, discretion of the investigator, SMC recommendation, subject is lost to follow up, and other.

Other subject listings will include a listing of inclusion and exclusion criteria violations, a listing of major protocol deviations, and a listing of screen failures with the reasons for screen failure.

12. Demographic and Baseline Characteristics

The demographic variables collected in this study include age, gender, race, and ethnicity. Subjects who record more than one race will be grouped into a single category denoted as multiple. Additionally, the number and percentage of subjects in each treatment group who are on background pirfenidone or nintedanib will be included. Demographic variables will be summarized for the Safety population.

Age (years) will be summarized by study drug, using continuous descriptive statistics. Age will be reported in years and calculated using the following formula:

$$\text{Age} = ((\text{consent date} - \text{date of birth}) / 365.25) \text{ truncated as an integer}$$

The number and percentage of subjects will be presented by treatment group, all GBT440, and all subjects.

The subject listing will include all demographic variables including the non-childbearing potential for female subjects.

13. Targeted Medical History, Other Medical History, and Concomitant Medications

13.1 Targeted Medical History

Medical history events identified as targeted medical history will be summarized with the number and percent of subjects in each treatment group, and for all GBT 440 subjects, who experienced each event. The targeted medical history events that will be summarized are as follows:

- Cancer (including cancer therapies and procedures)
- Inflammatory/Autoimmune Disorders
- Primary Hypertension (including grade of severity and medications taken)
- Pulmonary Rehabilitation
- Gastroesophageal Reflux (including medications taken)
- Sleep-Disordered Breathing/Sleep Apnea (including use of non-invasive ventilation, surgeries, and medications taken)
- Pulmonary Embolism (including medications taken)
- Lactose Intolerance (including medications taken)

Other medical history will be summarized using discrete summary statistics and will be presented by study drug at the subject and event level by System Organ Class (SOC) and Preferred Term (PT) using the Safety population. If a subject reports the same PT multiple times within the same SOC, that PT will only be reported once within that SOC. As with the PT, if a subject reports multiple conditions within the same SOC, that SOC will only be reported once. Other medical history will be coded using Medical Dictionary for Regulatory Activities (MedDRA), version 19.0.

All medical history data will be listed.

